### **1.3.2. Safety and Part B Expansion Dose for PF-06753512 (PrCa VBIR) combined with PF-06801591 (anti PD-L1 antibody)**

As of 11 November 2019, 69 participants had been enrolled in the B7791001 study in Cohorts 1A and 2A (n=7), which include escalating doses of AdC68 (PF-06755992) ranging from  $4 \times 10^{11}$  VP to  $6 \times 10^{11}$  VP and a fixed dose of pDNA (PF-06755990) of 5 mg; Cohorts 3A (n=6) and 1B (n=20), which include  $6 \times 10^{11}$  VP AdC68, 5 mg of pDNA, and 80 mg of tremelimumab; Cohort 6A (n=7) and 5B (n=12), which include  $6 \times 10^{11}$  VP AdC68, 5 mg of pDNA, 80 mg of tremelimumab, and 130 mg of PF-06801591; Cohort 9A (n=3), which includes  $6 \times 10^{11}$  VP AdC68, 5 mg of pDNA, 40 mg of tremelimumab and PF-06801591

130 mg; and Cohort 7A (n=14), which includes  $6 \times 10^{11}$  VP AdC68, 5 mg of pDNA, 80 mg of tremelimumab and PF-06801591 300 mg.

As of 11 November 2019, the most frequently experienced ( $\geq 5$  participants) treatment related AEs were fatigue and influenza like illness (27 participants; 39.1% each), diarrhoea (14 participants; 20.3%), nausea and pyrexia (10 participants; 14.5% each), decreased appetite, and myalgia (9 participants; 13.0% each), injection site pain, alanine aminotransferase increased, headache, and amylase increased (8 participants; 11.6% each), aspartate aminotransferase increased, lipase increased, and arthralgia (7 participants; 10.1% each), pruritus (6 participants; 8.7%), hyperthyroidism, hypothyroidism, abdominal pain, chills, vomiting, injection site discomfort, weight decreased, and hyponatraemia (5 participants; 7.2% each).

Adverse Drug Reactions (ADRs) identified for PrCa VBIR (PF-06753512) in combination with PF-06801591 include colitis and hypothyroidism.

## 1.4. Nonclinical Safety

### 1.4.1. Nonclinical Toxicity Study for PrCa VBIR

The nonclinical safety of the AdC68, plasmid DNA (pDNA) and tremelimumab were assessed in a repeat-dose toxicity study in sexually-mature male monkeys. The cynomolgus monkey was considered the appropriate species for the toxicity study because of the high homology (DNA/protein) of the three antigens between monkeys and humans, and because of the lack of activity of tremelimumab in rodents. The safety of AdC68 was also evaluated following a single dose administered without tremelimumab, as part of the repeat-dose study in monkeys. In a separate study, the tissue distribution and persistence of AdC68 was characterized using quantitative polymerase chain reaction (qPCR) following a single intramuscular injection in Cotton rats, a species that was demonstrated to express encoding antigens.

The repeat-dose toxicity study in monkeys used the same routes of administration and the same dose regimen for the vaccine components and tremelimumab as proposed for this study. An initial priming dose of AdC68 was followed by 3 consecutive boost doses with pDNA followed by an additional boost with AdC68, all administered at 28-day intervals.

Tremelimumab was administered by SC injection at a site local to the vaccine delivery site on the same days as vaccine administration. The absolute dose of AdC68 ( $6 \times 10^{11}$  VP) was the same as the highest proposed human dose. The absolute dose of plasmid DNA (10 mg) was two times the proposed human dose. Tremelimumab was evaluated at two dose levels (50 and 150 mg) when administered with the vaccine components, and at the 150 mg/dose level in the absence of the vaccine components, using the same monthly dosing regimen.

In the repeat dose study, there was no evidence of systemic toxicity and findings were limited to the injection sites and the draining lymph nodes and are consistent with a local inflammatory reaction and generation of an immune response. Mild non-adverse increases in monocytes, fibrinogen, thyroxine and marked increases in C-reactive protein consistent with an immune response associated with AdC68 administration were observed. There were no indications of local irritation (erythema or edema) attributed to the administration of AdC68, tremelimumab or AdC68/pDNA/tremelimumab noted over the course of the dosing and recovery periods of the study. Slight, transient increase in body temperature was noted 24 hours after administration of the pDNA/tremelimumab in one animal; however, no consistent pattern was observed.

### 1.4.2. Nonclinical Toxicity Studies of PrCa VBIR with PF-06801591

The safety and toxicokinetics of the PrCa VBIR in combination with SC or intravenous (IV) administered PF-06801591 was evaluated in a Good Laboratory Practice (GLP) study in sexually-mature male cynomolgus monkeys. PF-06801591 was administered at a dose of 20 mg/kg by SC or IV injection concurrently with the initial AdC68 prime dose and a single pDNA boost of the PrCa VBIR (2 injections, 1-month apart). SC injections were made at a site local to the vaccine delivery site, adjacent to the tremelimumab injection site. The safety of PF-06801591 administered by SC injection according to the same dose schedule in the absence of the PrCa VBIR was also evaluated as part of this study.

There were no microscopic findings, changes in clinical pathology parameters, or other evidence of local or systemic toxicity when PF-06801591 was administered alone at 20 mg/kg SC. There was no evidence of systemic toxicity when the PrCa VBIR was administered in combination with SC or IV dosages of PF-06801591. Mild, transient increases in globulin and moderate to marked increases in C-reactive protein (CRP) were observed following administration of the PrCa VBIR in combination with PF-06801591 on Days 1 and 28. Transient increases in lymphocytes and/or monocytes, and fibrinogen were observed following administration on Day 1 only (priming dose with AdC68). These changes were considered indicative of an inflammatory response to vaccine administration. Microscopic findings of minimal to mild chronic inflammation at the vaccine injection sites, and tremelimumab and PF-06801591 SC injection sites, were consistent with generation of an immune response against the vaccine components and localized effects at the injection sites. All effects were considered nonadverse, because they were transient and/or based on the low magnitude and absence of correlating adverse clinical pathologic alterations. Increases in antigen-specific T cells were observed in all animals that received the vaccine components with tremelimumab and PF-06801591. PF-06801591 exposures were similar on Days 1 and 29 when administered as a single agent by SC injection. PF-06801591 exposures were lower on Day 29 compared to Day 1 when co-administered with the PrCa VBIR, possibly due to induction of anti-drug antibodies (ADA). Tremelimumab exposures were similar when co-administered with SC or IV PF-06801591.

Results of cytokine release assays conducted using tremelimumab and PF-06801591 in combination in human whole blood or PBMCs showed no synergistic effect on cytokine release when these agents were combined, and thus, indicate a low risk of human cytokine toxicity.

## **1.5. Pharmacokinetics of Tremelimumab and PF-06801591**

### **1.5.1. Tremelimumab Pharmacokinetics After Intravenous Administration**

The single-dose and multiple-dose pharmacokinetics (PK) of tremelimumab following intravenous (IV) administration have been studied in participants with varied tumor types, including solid tumors, melanoma, and prostate cancer (Studies A3671001, A3671002 and A3671004). After IV administration, tremelimumab exhibited a biphasic disposition profile. Over the dose range of 0.1 to 15 mg/kg, mean values of the maximum drug concentration ( $C_{max}$ ) and the area under the concentration-time curve (AUC) increased with dose in an approximately proportional manner. Tremelimumab had a low clearance (mean values ranged from 0.119 to 0.152 mL/hr/kg), a small volume of distribution (mean values ranged from 78.1 to 85.1 mL/kg), and a long terminal disposition half-life ( $t_{1/2}$ ; mean values ranged from 19.2 to 24.8 days). After repeated administration at 10 mg/kg once every 4 weeks, the accumulation ratio based on AUC was approximately 1.26.

PK of tremelimumab after subcutaneous administration has not been evaluated in previous studies.

### 1.5.2. PF-06801591 Pharmacokinetics

Single and multiple dose PK of PF-06801591 are being evaluated in the ongoing Phase 1b/2 study B8011001 (Section 1.6.4.1). Preliminary PK data from Phase 1 cohorts suggest that PF-06801591 exhibits PK characteristics typical of IgG4 monoclonal antibodies.

The mean maximum serum concentration ( $C_{max}$ ) and area under the serum concentration-time curve over the dosing interval ( $AUC_{tau}$ ) of PF-06801591 increased in an approximately dose-proportional manner over the dose range of 0.5 -10 mg/kg following IV administration. The CV% values for  $C_{max}$  and  $AUC_{tau}$  were 24% to 35% and 22% to 36%, respectively (n = 2-8 per dose level), following the first IV dose. After SC administration at 300 mg, PF-06801591 was slowly absorbed, with a median  $T_{max}$  of approximately 8 days (n = 15). Steady state exposure after repeated SC dosing at 300 mg every 4 weeks fell within the range observed following IV dosing at 1 and 3 mg/kg, Q3W.

### 1.6. Starting Dose Rationale

Below are listed the rationales for the starting doses of the various components:

#### 1.6.1. Clinical Adenovirus C68 Dosing

Anticipated efficacy and safety were considered when selecting the AdC68 dose range for clinical testing. The dose ranges of  $1 \times 10^9$  VP to  $5 \times 10^{11}$  VP of a modified adenovirus antigen delivery system have shown a tolerable safety profile in patients with colorectal cancer as well as dose-dependent immune responses to a self-antigen. Previously, high doses of different adenovirus vectors were evaluated preclinically. The absence of germ line transmission was demonstrated in mice and baboons. In a separate study in NHPs, a dose of  $5 \times 10^{12}$  VP/kg was found to be well tolerated. Importantly, repeated administration did not appear to alter the toxicity/tolerability profile. It is also important to note that these animals were dosed IV per kg body weight, making the total dose substantially higher than the highest dose planned in this study ( $6 \times 10^{11}$  VP IM total dose). Furthermore, since the administration in this study is IM, the systemic safety profile is anticipated to be more favorable. Higher doses of adenovirus, up to  $2 \times 10^{11}$  VP/kg (total dose in excess of  $1 \times 10^{13}$  VP), when administered directly into the hepatic artery are tolerated in patients with partial ornithine transcarbamylase deficiency.

In the toxicity study of AdC68, plasmid DNA and tremelimumab in monkeys, the safety and antigen-specific T-cell responses were evaluated following administration of AdC68 at  $6 \times 10^{11}$  VP, either as a single agent or in combination with plasmid DNA and tremelimumab using the same dosing frequency as planned for the Phase 1 study. As described in [Nonclinical Safety](#), there was no evidence of systemic toxicity in the study and findings were limited to the injection sites and the draining lymph nodes. CCI

Based on the above safety and immune response data, a starting dose of  $4 \times 10^{11}$  VP administered IM has been selected as the starting dose for AdC68 in this study.

### **1.6.2. Clinical Plasmid DNA Dosing**

Efficacy and safety were factors considered to select the DNA dose for clinical testing. DNA doses of 0.2 to 8 mg have been reportedly delivered in clinical trials by other sponsors using the Ichor TDS electroporation device. In NHPs, the data collected to date demonstrated that electroporation of DNA dose at 5 mg can effectively and reproducibly boost AdC68 vector primed IFN $\gamma$  CD8 T cell responses to a self-antigen in the presence of tremelimumab. A DNA dose of 10 mg was well tolerated but no significant benefit on the magnitude or responder frequency of the IFN $\gamma$  CD8 T cell responses was observed. Thus, a dose of 5 mg is selected for the DNA for clinical testing.

### **1.6.3. Clinical Tremelimumab Dosing**

More than 1000 participants with cancer have been treated with tremelimumab as single-agent or in combination with another anti-cancer treatment. Clinical safety data for tremelimumab, at IV doses ranging from 0.01 to 15 mg/kg, indicate an acceptable safety profile in participants with cancer. The established maximum tolerated dose (MTD) for single-agent therapy is 15 mg/kg IV every 12 weeks, a dose level that has been extensively studied in a Phase 3 trial in participants with melanoma. Diarrhea, pruritus, and rash were the most common treatment-related adverse events (AEs) associated with tremelimumab. Another important event observed related to tremelimumab was hypopituitarism.

Monthly dosing, as planned for this study, was tested in the clinic in participants with melanoma, where administration of up to 10 mg/kg IV monthly was tolerated with no dose-limiting toxicity observed. The overall profile was found to be acceptable with the most frequent treatment-related AEs being diarrhea, rash, and pruritus. Frequency of Grade 3/4 AEs was 27% in the participants dosed with 10 mg/kg once every month.

The highest dose of tremelimumab will not exceed 150 mg, which equals to 2 mg/kg for a 75 kg patient, is expected to lead to a systemic exposure not exceeding that of a 2 mg/kg IV dose in a 75 kg patient. Thus, the AUC and Cmax of this dose are expected to be lower than those of the 10 mg/kg dose of tremelimumab previously administered to participants monthly via the IV route as described above.

Given the lower doses and the different route of administration, SC rather than IV administration, this study will start at a dose level of 80 mg total dose SC. In the event that 80 mg SC is not tolerated, lower dose levels (eg, 40 mg) may be tested.

### **1.6.4. Clinical PF-06801591 Dosing**

The starting dose of PF-06801591 will be at 130 mg, administered SC every 4 weeks (Q4W) in combination with the PrCa VBIR. Upon evaluation of the emerging safety (including late onset toxicities) and PK data of PF-06801591 from the initial PF-06801591 dosing cohort in all participants for 4 weeks or longer, a higher PF-06801591 dose of 300 mg was selected for further evaluation with escalating doses of tremelimumab. The specific dose level for PF-06801591 dosing cohorts was selected to achieve the systemic exposure that has shown to

be therapeutically effective for similar anti-PD-1 mAbs, not to exceed 300 mg due to the limitation of injection volume. The starting dose of 130 mg was selected based on data from nonclinical safety studies of PrCa VBIR in combination with PF-06801591, and known dose/exposure-response relationships of similar anti-PD-1 monoclonal antibodies. The steady-state  $C_{max}$  and  $AUC_{0-\tau}$ , following SC administration of PF-06801591 at 130 mg Q4W in humans, were predicted to be approximately 8% and 43%, respectively, of the  $C_{max}$  and  $AUC$  of the no observed adverse effect level (NOAEL) determined from the nonclinical safety study of the PrCa VBIR in combination with PF-06801591 in cynomolgus monkeys. Also, the predicted steady state  $C_{max}$  and average concentration ( $C_{average}$ ) of PF-06801591 at 130 mg Q4W are comparable or lower than those achieved by nivolumab or pembrolizumab at tolerated intravenous dose levels, either given alone or in combination with an anti-CTLA4 mAb (Keytruda [pembrolizumab] United States Package Insert (USPI) version 12/2015; Opdivo [nivolumab] USPI version 3/2015).

#### **1.6.4.1. PF-06801591, an Anti-PD-1 Antibody: Clinical Experience in Study B8011001 (NCT02573259)**

B8011001 is an ongoing Phase 1, open-label, multi-center, multiple-dose, dose escalation and expansion, safety, PK, and PD study of PF-06801591. The primary purpose of this study is to evaluate safety and early signs of efficacy. This clinical study was divided into a dose escalation (Part A) phase and a dose expansion (Part B) phase. One hundred forty-six participants have been dosed on the study. No dose limiting toxicity was observed and there was no maximum tolerated dose identified.

#### **Part A Dose Escalation**

Part A dose escalation evaluated 4 pre-specified IV dose levels (0.5, 1, 3, and 10 mg/kg administered every 3 weeks [Q3W]), and 1 subcutaneous (SC) dose level (300 mg administered every 4 weeks [Q4W]) in adult participants with locally advanced or metastatic melanoma, squamous cell cancer of head and neck, ovarian cancer, sarcoma, small cell lung cancer, adenocarcinoma of salivary gland, endometrial adenocarcinoma, malignant peritoneal neoplasm, esophageal adenocarcinoma or renal cell carcinoma. Participants had progressive disease on  $\geq 1$  prior line of therapy for locally advanced or metastatic disease or refused standard of care therapy; were not previously treated with an anti-PD-1/PD-L1 agent; and had adequate renal, bone marrow, liver, and cardiac function, with Eastern Cooperative Oncology Group (ECOG) performance status 0 or 1. Forty participants were enrolled into Part A with 25 participants total enrolled into the IV dose cohorts and 15 participants enrolled into the SC dose cohort.

#### **Part B Dose Expansion**

The 300 mg SC dose was evaluated in an expanded population of 106 participants. This included 68 participants with locally advanced or metastatic non-small cell lung cancer (NSCLC) and 38 participants with locally advanced or metastatic urothelial carcinoma who were anti-PD-1 or anti-PD-L1 treatment-naïve and who had progressive disease on or were intolerant to systemic therapy or for whom standard of care systemic therapy was refused or unavailable. Participants with NSCLC could have received up to 1 line of prior systemic

therapy for locally advanced or metastatic disease and if they had known epidermal growth factor receptor (EGFR) activating mutation or an anaplastic lymphoma kinase (ALK) rearrangement were required to have, in addition, at least 1 targeted therapy for their disease. Participants with UC could have received up to 2 lines of prior systemic therapies for locally advanced or metastatic disease. The selected participants had adequate renal, bone marrow, liver, and cardiac function, with ECOG performance status 0 or 1. All participants received 300 mg of PF-06801591 SC every 4 weeks.

Complete information for PrCa VBIR may be found in the single reference safety documents (SRSD). The SRSDs for this study are the PF-06753512 Investigator's Brochure for: AdC68 (PF-06755992), plasmid DNA (PF-06755990), PF-06801591, and tremelimumab.

The SRSD for the electroporation device is the Trigrid™ Delivery System electroporation device Investigator's Brochure.

Additional reference information can be found in the individual tremelimumab IB and the PF-06801591 IB.

## **2. STUDY OBJECTIVES AND ENDPOINTS**

### **2.1. Part A Objectives**

#### **Part A Primary Objective**

- To assess safety and tolerability of increasing dose levels of the prostate cancer vaccine-based immunotherapy regimen (PrCa VBIR) components alone and in combination with increasing doses of PF-06801591.
- To characterize the dose limiting toxicities (DLTs), if any are observed, and overall safety profile of escalated doses of the PrCa VBIR components alone and in combination with increasing doses of PF-06801591.
- To determine the Part B Expansion Dose for the PrCa VBIR components and PF-06801591 in combination.

#### **Part A Secondary Objectives**

- To evaluate the immune response elicited by the PrCa VBIR to the selected prostate cancer tumor-antigens.
- To evaluate the overall safety profile in prostate cancer participants.
- To evaluate the PK of tremelimumab after SC administration.
- To evaluate the PK of PF-06801591 after SC administration.
- To evaluate the anti-drug antibody (ADA) response of tremelimumab after SC administration with the other PrCa VBIR components.

- To evaluate the ADA response of PF-06801591 after SC administration with the other PrCa VBIR components.

## Part A Exploratory Objectives

- To document any preliminary evidence of anti-tumor activity.

[REDACTED]

[REDACTED]

## 2.2. Part A Endpoints

### Part A Primary Endpoint

- Incidence and grade of treatment-emergent adverse events including DLTs as graded by National Cancer Institute Common Terminology Criteria for Adverse Events (NCI CTCAE version 4.03).

### Part A Secondary Endpoints

- Immune response including T cells specific to the three selected prostate cancer tumor-antigens.
- Laboratory abnormalities as characterized by type, frequency, severity (as graded by NCI CTCAE v 4.03) and timing.
- Tremelimumab single-dose PK parameters, including the maximum concentration ( $C_{max}$ ), time to maximum concentration ( $T_{max}$ ), and area under the concentration versus time curve (AUC) from time zero to the last quantifiable time point prior to the second tremelimumab dose ( $AUC_{last}$ ) and if data permit, AUC from time zero extrapolated to infinity ( $AUC_{inf}$ ); and trough concentrations after multiple dosing ( $C_{trough}$ ).
- PF-06801591 single-dose PK parameters, including  $C_{max}$ ,  $T_{max}$ ,  $AUC_{last}$ , and if data permit,  $AUC_{inf}$ , and  $C_{trough}$  after multiple dosing.
- Incidence and titers of ADA and neutralizing antibodies against tremelimumab.
- Incidence and titers of ADA and neutralizing antibodies against PF-06801591.

[figure not shown]

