5. Blood samples for determination of tremelimumab drug concentrations and for detection of ADA against tremelimumab will be collected as outlined in the [schedule of activities](#). Samples to be collected on dosing days are to be obtained within 6 hours prior to tremelimumab dosing.
6. Blood samples for determination of PF-06801591 drug concentrations and for detection of ADA against PF-06801591 will be collected as outlined in the [schedule of activities](#). Samples to be collected on dosing days are to be obtained within 6 hours prior to PF-06801591 dosing.

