## **9.6. Analysis of Other Endpoints**

### **9.6.1. Pharmacokinetic Analyses**

#### **9.6.1.1. Tremelimumab Pharmacokinetics**

The concentration-time data of tremelimumab will be summarized by descriptive statistics (n, mean, standard deviation, median, minimum, and maximum) according to dosing cohort and time.

For patients of Cohort 3A, the concentration-time data of tremelimumab after the first dose will be analyzed individually by non-compartmental methods to determine the PK parameters. The PK parameters to be estimated will include the  $C_{max}$ ,  $T_{max}$ ,  $AUC_{last}$ , and if data permit,  $AUC_{inf}$ , terminal elimination half-life ( $t_{1/2}$ ), and apparent clearance (CL/F). In addition, the accumulation ratio (Rac) as calculated by the ratio of the trough concentration prior to the fifth tremelimumab dose (on Cycle 2 Day 1) to the concentration prior to the second tremelimumab dose (on Cycle 1, Day 29) will be determined individually if data permit. The PK parameters will be summarized using descriptive statistics according to dosing cohort.

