For patients of Cohorts 3A and 4A, the concentration-time data of tremelimumab after the first dose will be analyzed individually by non-compartmental methods to determine the PK parameters. For patients of Cohorts 6A through 9A, the concentration time data of PF-06801591 after the first dose will be analyzed individually by non compartmental methods to determine the PK parameters. For each compound, the PK parameters to be estimated will include the maximum drug concentration (C_{max}), time to maximum drug concentration (T_{max}), and area under the concentration versus time curve (AUC) from time zero to the last quantifiable time point prior to the second tremelimumab or PF-06801591 dose (AUC_{last}), and if data permit, AUC from time zero extrapolated to infinity (AUC_{inf}), terminal elimination half-life ($t_{1/2}$), and apparent clearance (CL/F). In addition, the accumulation ratio (Rac) as calculated by the ratio of the trough concentration prior to the fifth tremelimumab or PF-06801591 dose (on Cycle 2 Day 1) to the concentration prior to the second tremelimumab or PF-06801591 dose (on Cycle 1, Day 29) will be determined individually if data permit.

PK parameters will be calculated using standard non-compartmental methods:

Parameter	Method of Determination
AUC _{last}	Linear/log trapezoidal method
AUC _{inf} ^a	AUC _{last} + (C _{last*} /k _{el}), where C _{last*} is the predicted concentration at the last quantifiable time point (T) estimated from the log-linear regression analysis, and k _{el} is the terminal phase rate constant calculated by a linear regression of the log-linear concentration-time curve. The terminal log-linear phase will be determined from a minimum of 3 concentration-time data points, and will be verified with the r ² value.
C _{max}	Observed directly from data
CL/F ^a	Dose/AUC _{inf}
t _{1/2} ^a	ln2/k _{el}
T _{max}	Observed directly from data

^a if data permit.

The PK parameters of each compound will be summarized as below:

[figure not shown]
Parameter	Summary statistics
AUClast, AUC _{inf} , C _{max} , and CL/F	N, arithmetic mean, median, cv%, standard deviation, minimum, maximum, geometric mean.
t _{1/2}	N, arithmetic mean, median, cv%, standard deviation, minimum, maximum.
T _{max}	N, median, minimum, maximum.

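### The protocol ties the tremelimumab accumulation ratio to Cohort 3A (n=6) and the SAP leaves its cohorts unclear, although the two troughs it needs are scheduled in about 77 more participants

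*Protocol*

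**What the plan says.** The Part A secondary endpoints in Protocol 2.2 list "Tremelimumab single-dose PK parameters, including the maximum concentration", the other first-dose parameters and the trough after multiple dosing; they name no accumulation ratio.

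Protocol 9.6.1.1 first has tremelimumab concentrations summarised for every dosing cohort by time. It then turns to derived parameters: "For patients of Cohort 3A, the concentration-time data of tremelimumab after the first dose will be analyzed individually by non-compartmental methods". The same paragraph goes on to define "the accumulation ratio (Rac) as calculated by the ratio of the trough concentration prior to the fifth tremelimumab dose" over the concentration before the second dose, to be determined per participant if data permit. Protocol 9.6.1.2 has the same structure for PF-06801591, with Cohorts 6A to 9A in place of 3A.

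SAP 8.1.5.1 differs: "For patients of Cohorts 3A and 4A, the concentration-time data of tremelimumab after the first dose will be analyzed individually by non-compartmental methods". It then names 6A to 9A for PF-06801591. One Rac sentence follows for both compounds and repeats no cohort limit. Rac has no row in the SAP's tables of parameter methods and summary statistics.

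Protocol 1.3.2 gives the cohort sizes at 11 November 2019, including "Cohorts 3A (n=6) and 1B (n=20), which include" the tremelimumab regimen without PF-06801591. Cohort 4A is not in that list, and no PK sampling table is given for it. The treatment and PK schedules place tremelimumab samples on Cycle 1 Day 29 and Cycle 2 Day 1 in 3A, 6A to 9A, 1B, 3B and 5B. For 3B and 5B the footnote reads: "Samples to be collected on dosing days are to be obtained within 6 hours prior to tremelimumab dosing".

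**The concern.** Protocol 1.5.1 states that "PK of tremelimumab after subcutaneous administration has not been evaluated in previous studies", so what the trial learns about accumulation by this route is new information. Read literally, the protocol takes the paired estimate from six participants who received no PF-06801591 and derives none for the combination regimens given in 3B and 5B. Rac needs only two pre-dose samples, and both are already on the schedule in the other tremelimumab cohorts.

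The planned summaries by cohort and nominal time do not give the same information. They are unpaired: a participant who stops before Cycle 2 Day 1 contributes to the Day 29 mean but not to the later one, so a ratio of the two means mixes accumulation with a change in who is measured.

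The protocol and SAP also disagree. Two programmers could produce different Rac tables, one from 3A alone and one from every cohort with both samples, and each could point to supporting text.

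**Working it through.** **Inputs.** Protocol 1.3.2 gives 1A and 2A 7, 3A 6, 1B 20, 6A 7, 5B 12, 9A 3 and 7A 14. Protocol 3.1.2 gives later counts of 15 for 5B and 18 for 3B. The documents give no CV for Rac, no rate of reaching Cycle 2 Day 1 and no precision target, so the CV and attrition below are assumptions.

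**The plan's own figure.** 7 + 6 + 20 + 7 + 12 + 3 + 14 = 69, which matches the stated enrolment and leaves no room for a Cohort 4A participant at that date.

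**Participants with both troughs scheduled.**
- Tremelimumab outside 3A: 20 + 7 + 14 + 3 + 18 + 15 = 77; with 3A, 83. (Amendment 8 cites 33 for two mCRPC cohorts. If these are 7A and 3B, 7A is 15 and the totals rise by one.)
- PF-06801591: 7 + 14 + 3 = 24 in 6A to 9A, plus 18 + 15 = 33 in 3B and 5B, giving 57.

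**By regimen.**
- Tremelimumab 80 mg without PF-06801591 (3A, 1B): 6 + 20 = 26.
- 80 mg with PF-06801591 130 mg (6A, 5B): 7 + 15 = 22.
- 80 mg with 300 mg (7A, 3B): 14 + 18 = 32.
- 40 mg with 130 mg (9A): 3.

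**Precision.** With s = sqrt(ln(1 + CV²)), the 95% CI for the geometric mean Rac is the estimate multiplied and divided by exp(t(0.975, n−1) × s / sqrt(n)). At CV 40%, s = sqrt(ln 1.16) = 0.385.
- n = 6: 2.571 × 0.385 / sqrt(6) = 0.404, factor 1.50.
- n = 26: 2.060 × 0.385 / sqrt(26) = 0.156, factor 1.17.
- n = 22: 2.080 × 0.385 / sqrt(22) = 0.171, factor 1.19.
- n = 32: 2.040 × 0.385 / sqrt(32) = 0.139, factor 1.15.

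At CV 30% (s = 0.294) the factors are 1.36 for n = 6 and 1.13 for n = 26. At CV 50% (s = 0.472) they are 1.64 and 1.21.

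**Dropout.** These figures assume that everyone contributes a pair. If two-thirds do, 3A has 4 pairs (3.182 × 0.385 / sqrt(4) = 0.613, factor 1.85) and 3A plus 1B has about 17 (2.120 × 0.385 / sqrt(17) = 0.198, factor 1.22). Both intervals widen, and the gap remains.

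**Scale.** Protocol 1.5.1 reports an intravenous accumulation ratio of about 1.26. It is AUC-based and from another route, so it serves only as a reference. Were the subcutaneous Rac 1.26, the interval at CV 40% would be 0.84 to 1.89 with n = 6, which includes no accumulation, and 1.08 to 1.47 with n = 26.

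**Single-dose parameters.** Tremelimumab samples on Days 3 to 6, 8, 15 and 22 are scheduled only in 3A. In 6A to 9A those draws are for PF-06801591. The extra 77 participants therefore add nothing to tremelimumab Cmax, Tmax, AUC, half-life or CL/F.

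**The case against.** A reader might infer that the whole subcutaneous tremelimumab PK analysis is needlessly confined to six participants. The documents do not support that. Cmax, Tmax, AUC, half-life and CL/F need post-dose samples that only 3A has, so that restriction follows the sampling design.

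Nor are data from the other 77 ignored. Protocol 9.6.1.1 and SAP 8.1.5.1 summarise concentrations in every cohort, and the SAP lists each participant's values by nominal time, so the two troughs can be read off. What is missing is the derived, paired summary.

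Rac is descriptive, absent from the visible endpoint lists and qualified by data availability. The listed multiple-dose endpoint is the trough concentration, which all these cohorts supply. No hypothesis test or stated decision rule rests on Rac. All of this stands, and it limits how much the point matters.

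The SAP's Rac sentence can fairly be read as covering any cohort with both samples, and Protocol section 9 lets the SAP modify the protocol's plans. That stands too, and it is a reason to state the scope.

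Full pooling would mix 40 mg with 80 mg and regimens with and without PF-06801591, so regimen-level reporting should come first. A paired ratio does not remove selection by dropout either: it describes only those who reach Cycle 2 Day 1, though numerator and denominator then come from the same people. Redacted text near the PK sections may hold further analyses, which can be neither assumed nor excluded.

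**Conclusion.** The point holds for the accumulation ratio only. The protocol's text limits tremelimumab Rac to six participants and PF-06801591 Rac to 24, the SAP's scope is ambiguous, and its mention of 4A has no counterpart in Protocol 9.6.1.1 or the enrolment list. Using troughs already scheduled would raise the same-regimen tremelimumab group from 6 to 26 and, at an assumed CV of 40%, cut the CI factor from 1.50 to 1.17. Over CVs of 30% to 50% it falls from 1.36–1.64 to 1.13–1.21. These figures assume complete pairs; dropout before Cycle 2 Day 1, which the documents do not quantify, would widen both.

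The larger gain may be a paired estimate for the combination regimens (22 and 32 participants before dropout), for which the protocol's text derives no tremelimumab Rac. This is an inexpensive improvement to a descriptive analysis. It is not a defect in the primary or listed secondary endpoints.

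**What to change.** State in Protocol 9.6.1.1 and 9.6.1.2 and in SAP 8.1.5.1 that Rac is derived for every participant with quantifiable pre-dose samples at Cycle 1 Day 29 and Cycle 2 Day 1 and an unchanged dose of the compound, in all cohorts receiving it. The samples must be quantifiable because SAP 7.3 sets values below the limit to zero, which a geometric mean of ratios cannot use.

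Report the number of pairs, the number of participants without a usable pair, and the geometric mean with 95% CI, by regimen first (for example 3A with 1B). Pool across regimens only as a secondary summary. Add a Rac row to the SAP's parameter tables. Make the cohort lists agree, either removing 4A or explaining it. Leave the single-dose parameters limited to 3A for tremelimumab.

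The cost is a few sentences and one table, with no new samples or assays.
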